**Statistical Analysis Plan (SAP):** We will apply 2 main forms of statistical analyses a) to report the pre-post changes in mean terms, and b) to report the results according with the inter-individual responses based on the technical error criteria, where according with the error calculated in the three previous measurements registered by the sample that was voluntary. Graph pad Prisma statistical software 8.0 (San Diego, CA, USA) will be used. The normal distribution of all the variables were tested using the Shapiro-Wilk test. Data will be presented as the mean and (95%CI) in tables, as mean

with ( $\pm$ ) standard error in Figures 1, 2, and 3, and as individual delta in Figure 4 for identification of Rs and NRs. Normality and homoscedasticity assumptions for all data were analysed using the Shapiro–Wilk and Levene’s test, respectively. In the HIIT+RT group, the Tg outcome, as well as in the RT+HIIT group, LDL-c, and lean mass outcomes were analysed by the *Wilcoxon* non-parametric test. For training-induced changes, the student’s *t* test was used to identify differences at baseline, while a repeated measure two-way ANOVA was applied to assess the occurrence of an actual training effect; namely,  $p < 0.05$  for the interaction (time x group) on the main MetS (WC, SBP, DBP, FPG, HDL, and Tg, as well as to the secondary outcomes). A Sidack’s post hoc test was used for multiple comparisons. Additionally, the Eta partial squared for interaction (Time x Group) was assessed by  $\eta^2$  obtained from the ANCOVA with small ( $\eta^2=0.01$ ), medium ( $\eta^2=0.06$ ), and large ( $\eta^2=0.14$ ) effects defined according to (Lakens, 2013). The prevalence of NRs was described using the comparisons by percentage between both experimental groups using a Chi square test  $\chi^2$ . All statistical analyses were performed with SPSS statistical software version 23.0 (SPSSTM Inc., Chicago, IL). The alpha level was set at  $p < 0.05$  for statistical significance.

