Campillo et al. 2017), have been described. In addition, considering the health-related benefits of CT including MICT/or HIIT plus RT in terms of physical fitness, and the metabolic markers in different populations, as well as taking into account the previous discrepancies of the order session in relevant literature, it is necessary to investigate the exercise modalities interaction as a precision medicine for improving MetS markers. This study will follow the CONSORT guidelines for randomised trials, will be developed in accordance with the Declaration of Helsinki (2013), and has been approved by the Ethical Committee of the Universidad de La Frontera, Temuco, Chile (DI18-0043 Project).

**Design:** An experimental, and randomized control clinical study. **Methods:** This study is a parallel-group randomised controlled trial in which 43 women with morbid obesity that will be randomly allocated to one of the two similar CT exercise programmes. The exercises will be applied in different session order by the two groups (HIIT+RT,  $n=17$ ), and resistance training plus high-intensity interval training (RT+HIIT,  $n=17$ ). All volunteers will read and signed an informed consent. The inclusion criteria will be; (i) being a candidate for bariatric surgery, (ii) aged between 18 and 60 years, (iii) being medically authorised, and (iii) with a body mass index (BMI)  $\geq 40$  kg/m^2 or  $\geq 35$  kg/m^2 with additional comorbidities (i.e. diabetes, hypertension, insulin resistance) controlled by pharmacotherapy according to the Chilean requirements for morbidly obese patients in order to be a candidate for bariatric surgery. The exclusion criteria will be; (i) having physical limitations preventing the performance of exercise (e.g. restricting injuries of the musculoskeletal system), (ii) having exercise-related dyspnoea or respiratory alterations, (iii) having chronic heart disease with any worsening in the last month, and (iv) adhering to less than 80% of the total interventions (these results were excluded from the statistical analyses).

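### Wilcoxon tests are assigned arm by arm, apparently after the data were inspected; they cannot compare the session orders, and their relation to the time-by-group ANOVA is not stated

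*Combined protocol and SAP*

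**What the plan says.** All of this stands in the Statistical Analysis Plan (SAP) paragraph.

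- One of its two main forms of analysis is "to report the pre-post changes in mean terms".
- Assumptions are checked on the variables themselves: "Normality and homoscedasticity assumptions for all data were analysed using the" Shapiro–Wilk and Levene tests.
- The next sentence reads "In the HIIT+RT group, the Tg outcome, as well as in the RT+HIIT group, LDL-c, and lean mass outcomes were analysed by the" Wilcoxon test. No selection rule is written. The SAP does not say whether signed-rank or rank-sum is meant, and it does not name the test for Tg in RT+HIIT or for LDL-c and lean mass in HIIT+RT.
- The sentence after that turns to the whole trial: "a repeated measure two-way ANOVA was applied to assess the occurrence of an actual training effect", judged at p<0.05 "for the interaction (time x group) on the main MetS (WC, SBP, DBP, FPG, HDL, and Tg, as well as to the secondary outcomes". Tg is named there. LDL-c and lean mass are covered only if they are secondary outcomes, and the documents never list those.
- The effect size for the interaction is said to come from an ANCOVA, with no covariate given.

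No rank-based between-arm test appears anywhere.

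**The concern.** The trial asks whether the order of HIIT and resistance training within a session matters. Only a contrast between the two arms answers that. A Wilcoxon test confined to one arm compares before with after in that arm and contains no such contrast.

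The allocation of tests also looks data-driven. It comes straight after the normality check, names a different set of outcomes in each arm, and has no design-based reason. Rewriting it in the future tense would not cure this, because the list itself depends on what each arm's data looked like.

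Tg, a main metabolic syndrome outcome, thus sits under two treatments: a rank test in one arm, presumably because normality looked doubtful, and an ANOVA that assumes normality across both. The SAP does not say which governs. A reader given a p-value from one test in one arm and from another test in the other could easily take a significant result in one order only as evidence that order matters.

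**Working it through.** The SAP gives no SD, effect size or power for any outcome, so there is no stated figure to reproduce. The check is of the logic, with assumed distributions.

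**Inputs from the documents.** 17 women per arm (Methods) and a significance level of 0.05 (SAP; taken as two-sided, which is not stated). The Methods also give 43 women in total against 17 + 17 = 34; that is a separate matter and does not alter the reasoning here.

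**Step 1: can two like arms be sent to different tests by chance?** If Shapiro–Wilk rejects with probability p in each of two arms from the same population, exactly one arm rejects with probability 2p(1−p). Simulated at n=17, 4,000 runs:

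| Assumed distribution | p | 2p(1−p) | Simulated |
|---|---|---|---|
| Normal | 0.046 | 0.09 | 0.09 |
| Lognormal, log-SD 0.3 | 0.197 | 0.32 | 0.31 |
| Lognormal, log-SD 0.5 | 0.440 | 0.49 | 0.49 |
| Lognormal, log-SD 0.7 | 0.666 | 0.44 | 0.44 |

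For a skewed outcome, different tests in the two arms are therefore unremarkable even when the arms do not differ.

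**Step 2: what happens if within-arm verdicts are set side by side?** Give both arms the same true change. If the arms have power a and b, their verdicts disagree with probability a(1−b) + b(1−a). With Wilcoxon in one arm, a paired t-test in the other, and normally distributed changes (4,000 runs):

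| Common change (SD of change) | a (Wilcoxon) | b (t) | Formula | Simulated disagreement |
|---|---|---|---|---|
| 0 | 0.042 | 0.057 | 0.09 | 0.09 |
| 0.25 | 0.145 | 0.162 | 0.26 | 0.26 |
| 0.5 | 0.460 | 0.501 | 0.50 | 0.50 |
| 0.7 | 0.732 | 0.783 | 0.37 | 0.36 |
| 1.0 | 0.963 | 0.974 | 0.06 | 0.06 |

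In the same runs a direct between-arm test of change rejected in 4.8–5.1% of trials, and Mann–Whitney on the changes in 4.5–5.0%. With two time points, the between-arm t-test of change is the time-by-group interaction.

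**Step 3: is Wilcoxon the cause?** No. With the t-test in both arms at 0.5 SD, disagreement would be 2 × 0.501 × 0.499 = 0.50, the same as with mixed tests. With lognormal Tg (log-SD 0.4–0.5, pre-post correlation 0.6–0.8, all assumed), the one-arm-significant pattern appeared in 14–49% of trials when a normality test chose between t and Wilcoxon, and in 13–49% with a paired t-test in both arms. The rate depends mainly on the within-arm power, so it varies with the common change assumed. For log changes of −0.10 to −0.20, that is falls of 1−e^(−0.10) ≈ 10% to 1−e^(−0.20) ≈ 18%, it is 22–50%.

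**Step 4: does the planned interaction test hold its level?** Yes. On raw lognormal Tg with equal log changes it rejected in about 4–6% of trials.

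**Step 5: what would a single better model gain?** On the log scale with equal variances, a change score has variance 2σ²(1−ρ), while the baseline-adjusted post value has residual variance σ²(1−ρ²). The ratio is (1+ρ)/2, which is 0.80 at ρ=0.6 and 0.90 at ρ=0.8. Adjustment thus removes 10–20% of the variance before any gain from the log scale. For an assumed log difference of 0.3 between arms, simulated power rose from 36–81% (raw-scale interaction) to 54–93% (baseline-adjusted model on log Tg). The false-positive rate of the latter was 4.0–5.6%.

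**The case against.** The strongest defence is that the order comparison is already in the plan. The sentence after the Wilcoxon list applies the time-by-group test to Tg by name and to the secondary outcomes, and makes that interaction the criterion for a training effect. Since one main form of analysis is pre-post change, Wilcoxon may be no more than a within-arm supplement where an arm looked non-normal. Nothing says that it replaces the ANOVA, and no sentence plans to contrast within-arm results. The normality trigger is itself inferred from the order of the sentences.

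Much of this stands. A reader might infer that these three outcomes have no comparison of session orders. The text does not support that for Tg, nor for LDL-c and lean mass if they are secondary outcomes. A reader might also infer that the 5% level of the planned between-order test is lost, or that arm-specific Wilcoxon selection produces the 14–49%. Steps 3 and 4 show neither.

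The defence does not dispose of the rest. The supplementary reading is plausible but unwritten, the other arm's test is still unnamed, and a list that differs by arm still has no explanation other than inspection of the data.

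**Conclusion.** The concern holds in a limited form. The SAP assigns Wilcoxon by arm, apparently after normality was inspected; a one-arm test cannot compare session orders; and the SAP neither relates it to the ANOVA nor names a between-arm rank-based alternative. The harm is one of interpretation. If the within-arm p-values are set side by side, identical true changes give a false appearance of an order effect in roughly 14–49% of trials at 17 per arm. That is a hazard of any within-arm comparison, and the planned interaction test avoids it.

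The percentages rest on assumed lognormal Tg and assumed changes, since the documents give none. The ambiguity about which test governs rests on the text alone. This should be fixed, but it does not leave the trial without a valid comparison for Tg.

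**What to change.** - Delete the arm-specific Wilcoxon sentence and the use of normality tests to choose the analysis.
- State that one between-arm model governs every outcome in both arms: post value = β0 + β1 × arm + β2 × baseline value, with Tg on the log scale. Report β1 as the HIIT+RT minus RT+HIIT difference (a ratio for Tg) with its 95% CI.
- Check the residuals of that model, not the raw variables.
- Add one between-arm rank-based or permutation analysis, the same for all outcomes, as a sensitivity analysis.
- List the secondary outcomes, so that it is clear whether LDL-c and lean mass are covered.
- Label all within-arm tests descriptive, and any Wilcoxon results already produced post hoc.

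A single sentence giving the existing interaction precedence would remove the ambiguity, but it would forgo the gain in power. The cost of the full change is SAP wording and standard model runs, with no new data. The one drawback is that Tg effects are reported as ratios and not as differences in original units.

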In addition, part of our preliminary findings have shown that 20 weeks of RT decreases MetS risk factors in morbidly obese patients, showing a low inter-individual variability those patients with greater adiposity, revealing that with more adiposity alteration, the benefits of RT are also more visible (Delgado-Floody, Alvarez et al. 2019). However, some inconsistencies have been described after CT, that are directly related with the 'order' (i.e. starting the CT session with MICT followed by RT, or vice versa) of the CT session. For example, some literature reports that by starting the exercise session with RT, participants can get more benefits and improve their physical fitness markers (i.e. increases of upper body strength and neuromuscular markers) (Murlasits, Kneffel et al. 2018). However, in contrast, other studies have reported that starting CT with MICT/or HIIT does not alter physiological adaptations in similar outcomes (Wilhelm, Rech et al. 2014). Other evidence shows that starting CT with firstly RT exercises clearly promotes greater lower-body strength gains and neuromuscular economy (Cadore, Izquierdo et al. 2013). By contrast, other reports claim no more benefits by starting with MICT/HIIT or RT to physical fitness markers in populations of athletes (Eddens, van Someren et al. 2018), and additionally, no additional benefits for decreasing body fat using one or another exercise modality when starting the CT session (Cadore, Izquierdo et al. 2012). However, little is known about the interindividual variability of exercise training (IVET) in relation to different order session of CT in morbidly obese populations, and in health-related outcomes, such as MetS markers. Briefly, IVET means that some subjects achieve benefits after training, and are termed responders (Rs), while others exhibit a worsened or unchanged response, that are commonly known as nonresponders (NRs) (Bouchard, Blair et al. 2012). With regard to the causes of IVET, genetic (Stephens, Xie et al. 2015), and environmental factors including the mode of exercise training (Alvarez, Ramirez-

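### The SAP's rule for a training effect is the time x group interaction, but both described arms train, so the rule tests session order and cannot detect a benefit the arms share

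*Combined protocol and SAP*

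**What the plan says.** The Statistical Analysis Plan (SAP) section has two strands. The first is "to report the pre-post changes in mean terms"; the second is a responder analysis based on technical error. For the first strand it says that "a repeated measure two-way ANOVA was applied to assess the occurrence of an actual training effect", and the same sentence spells out what counts as such an effect: p<0.05 "for the interaction (time x group) on the main MetS (WC, SBP, DBP, FPG, HDL, and Tg", and likewise for the secondary outcomes. The overall significance level is 0.05.

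The Design and Methods paragraph describes a parallel-group trial "in which 43 women with morbid obesity that will be randomly allocated to one of the two similar CT exercise programmes". On how the arms differ it says: "The exercises will be applied in different session order by the two groups". The arms are HIIT+RT and RT+HIIT, each listed with n=17. No non-exercising arm is described.

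The Scientific background presents the research gap as one about order: little is known about individual variability in response "in relation to different order session of CT in morbidly obese populations".

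**The concern.** The SAP's only stated rule for declaring a training effect is a contrast between two trained groups. Any change the groups share drops out of that contrast. The rule can therefore mislead in two ways:

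- Both orders work equally well. The rule then reports no training effect, apart from false positives at the significance level.
- The orders differ. The rule then labels an order difference as a training effect, even if one arm did not change at all.

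The rule governs all six main outcomes (WC, SBP, DBP, FPG, HDL, Tg). Because pre-post changes are reported as well, a benefit would not be hidden. But one report could show a clear pre-post improvement and, by the SAP's own rule, no training effect. The reader would have no stated basis for choosing between the two.

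**Working it through.** The plan gives no power calculation, SD or expected effect, so there is no figure of its own to reproduce.

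**Inputs from the documents**
- Criterion: time x group, p<0.05 (SAP).
- Arms: two, both trained, in different session order (Design and Methods).
- Numbers: 43 women in total, but 17 + 17 = 34 in the listed arms (Design and Methods). Both are used below.

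**Assumptions**
- One pre and one post measurement per woman.
- Normally distributed change scores with a common SD, set to 1, so effects are in SD of change.
- 22/21 as a near-equal split of 43.

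**Step 1: what the interaction estimates.** Let the true mean changes be d1 and d2. With two arms and two time points, the time x group F statistic is the square of the pooled two-sample t statistic on change scores:

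t = (mean change 1 − mean change 2) / [s·√(1/n1 + 1/n2)], with n1 + n2 − 2 degrees of freedom.

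Its target is d1 − d2. If d1 = d2 = d, the target is 0 for every d, and the rejection probability is the significance level, 5%.

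A simulation with 20,000 replicates per scenario agrees. It used equal changes of 0, 0.5 and 1 baseline SD, pre-post correlations of 0.5, 0.7 and 0.9, and 17/17 or 21/22 women. The interaction rejected in 4.6% to 5.4% of runs in every scenario.

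**Step 2: it responds only to the gap between arms.** At 17/17 and correlation 0.7, three patterns with the same gap of 0.5 baseline SD gave nearly the same interaction rejection rate:

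| Change in arm 1, arm 2 (baseline SD) | Interaction significant |
|---|---|
| −0.5, 0 | 44.4% |
| 0, +0.5 | 44.2% |
| −0.8, −0.3 | 45.2% |

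In the first two patterns one arm does not change at all. In the third both do.

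**Step 3: the time effect under the same equal benefit.** The time effect is (mean change 1 + mean change 2)/2, with standard error 0.5·√(1/n1 + 1/n2).
- 17/17: 0.5·√(2/17) = 0.171, df 32.
- 22/21: 0.5·√(1/22 + 1/21) = 0.153, df 41.

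Power is from the noncentral t distribution, two-sided 5%:

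| Shared benefit (SD of change) | Time effect, 17/17 | Time effect, 22/21 | Interaction, either N |
|---|---|---|---|
| 0.3 | 40% | 48% | 5% |
| 0.5 | 81% | 89% | 5% |
| 0.8 | 99.5% | 99.9% | 5% |

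**Step 4: how often the two disagree.** The chance that the time effect is significant while the SAP's rule is not met, from 200,000 simulations under equal benefit:
- 0.5 SD: 0.767 at 17/17 and 0.848 at 22/21.
- 0.8 SD: 0.946 and 0.949.

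These are close to the time-effect power times 0.95 (for example 0.807 × 0.95 = 0.767).

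**Step 5: precision of the order contrast.** The 95% CI half-width is t(0.975)·√(1/n1 + 1/n2):
- 17/17: 2.037 × √(2/17) = 0.70 SD of change.
- 22/21: 2.020 × √(1/22 + 1/21) = 0.62 SD of change.

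**The case against.** The best defence is that the test is sound and only its label is wrong. In a trial of session order, time x group is the right contrast, and the phrase about a training effect may be loose English for a differential effect. The ANOVA, the data and the p-values would not change. This largely stands as a description of the defect. It does not remove it, because the sentence equates the training effect with the interaction p-value, and a reader who follows it as written reaches the wrong conclusion.

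Second, within-arm information is planned. Pre-post change is one of the SAP's main analyses. The Wilcoxon tests are assigned arm by arm and look like paired tests, though the SAP does not say so. A Sidak post hoc test follows, and the ANOVA yields a time effect as routine output. This lowers the practical risk. But none of these is named as the criterion for a training effect, and the comparisons covered by the Sidak test are not specified.

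Third, the 5% figure is simply the significance level under a null interaction, and the disagreement rates in Step 4 are roughly the time-effect power times 0.95. Both points are correct. The figures show what the rule does in practice and are not separate evidence.

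Fourth, 43 − 34 leaves 9 women unaccounted for. If they were an undescribed untrained arm, the interaction would partly test training. In a hypothetical 17/17/9 layout with correlation 0.7, it was significant in 30% of simulations when the trained arms changed by 0.5 baseline SD, and in 85% at 1 SD. But the Methods allocate all 43 women to one of two training programmes, so this reading has no support in the text.

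**Conclusion.** The concern holds. As written, the SAP's criterion for a training effect is a test of session order, and it cannot detect a benefit common to both arms beyond the 5% false-positive rate per outcome. That result does not depend on effect size, pre-post correlation or which N applies; it needs only the usual ANOVA assumptions and the two trained arms the document describes.

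The size of the practical conflict does rest on assumed effects in SD of change. With a shared benefit of 0.5 SD, the time effect and the rule would point in different directions in about 77% (17/17) to 85% (22/21) of trials; at 0.8 SD, in about 95% at either N.

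The fault lies in the stated conclusion, since the contrast itself is appropriate and pre-post changes will be visible. It should be fixed because the rule decides what may be claimed for all six main outcomes.

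**What to change.** Reword the criterion in the SAP:

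- State that time x group is the test of session order. Report it for each outcome as the between-arm difference in mean change with a 95% CI.
- Report the time effect as pre-post change. Label it uncontrolled and do not use it to claim a causal effect of training: without an untrained arm it cannot be separated from the passage of time or regression to the mean.
- Give the interval when the order contrast is not significant, so that the result is not read as showing the orders equivalent. On the assumptions above, its half-width would be about 0.70 SD of change at 17/17 or 0.62 at 22/21.
- State which comparisons the Sidak test covers, and whether the analysis N is 34 or 43.

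The cost is a few sentences of SAP wording and one interval per outcome, with no new data. The price is a weaker training claim, because it would rest openly on an uncontrolled pre-post change.

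### The between-arm test is a t test on change that leaves the collected baseline out as a covariate; a post-on-baseline ANCOVA would usually be more precise, and the effect size should come from the same model as the p value

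*Combined protocol and SAP*

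**What the plan says.** All of this is in the Statistical Analysis Plan (SAP) paragraph unless noted.

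- **Between-arm test.** The plan says "a repeated measure two-way ANOVA was applied to assess the occurrence of an actual training effect", with the criterion p<0.05 "for the interaction (time x group) on the main MetS (WC, SBP, DBP, FPG, HDL, and Tg, as well as to the secondary outcomes". The mean analysis concerns pre-post change, so there are two time points. A Sidak post hoc test follows.
- **Effect size.** For the same interaction, the plan says that "the Eta partial squared for interaction (Time x Group) was assessed by" an eta-squared "obtained from the ANCOVA with small", medium and large cut-offs of 0.01, 0.06 and 0.14. This is the only mention of ANCOVA in the documents. No response, covariate or model term is given.
- **Baseline.** A Student's "test was used to identify differences at baseline". No consequence of the result is stated, and no model has baseline as a covariate.
- **Non-normal outcomes.** "In the HIIT+RT group, the Tg outcome, as well as in the RT+HIIT group, LDL-c, and lean mass outcomes were analysed by the" Wilcoxon test. No rule is given for the between-arm comparison of these outcomes.
- **Numbers (Design and Methods paragraph).** 43 women are to be randomised, but the arms are listed as 17 and 17. One listed exclusion is "adhering to less than 80% of the total interventions (these results were excluded from the statistical analyses". It is not said whether 34 is the count before or after this exclusion.

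**The concern.** With a single pre and a single post value, the interaction test compares mean change between arms. It subtracts each woman's baseline in full, as if the slope of post on baseline were exactly 1. When the true slope differs from 1, two things follow. The comparison usually carries more variance than one that estimates the slope. And in a trial where the arms differ at baseline by chance, the estimated difference moves by (1 - slope) times the gap.

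With arms of about 17, chance gaps of some size are common and precision is scarce, so a covariate already in the data set is worth using.

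The second, smaller matter is legibility. As written, the p value and the small, medium or large label for the same interaction are attributed to differently named models, and one of them is not specified.

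**Working it through.** The documents give no power calculation, SD, correlation or target effect, so there is no planned figure to reproduce. Inputs from the documents: 17 per arm (N = 34), 43 randomised, two time points, alpha 0.05 (taken as two-sided). Assumed: pre-post correlation rho of 0.5, 0.7, 0.8 or 0.9; post SD / baseline SD ratio k of 1, 0.8 or 1.25; normal baseline; a common slope.

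**1. The interaction test is a t test on change.** In a simulated data set with 17 per arm, the repeated-measures interaction F and the squared t on change were both 1.0967, and partial eta-squared was F/(F+32) both ways.

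**2. Variance of the arm difference.**
Change score: proportional to 1 + k² - 2·rho·k.
ANCOVA, in expectation: proportional to k²(1 - rho²)·[1 + 1/(N-4)].
Example, k = 1, rho = 0.5, N = 34: 0.75 × 1.0333 / 1 = 0.775.

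| ANCOVA / change variance, N = 34 | rho 0.5 | 0.7 | 0.8 | 0.9 |
|---|---|---|---|---|
| equal SDs | 0.78 | 0.88 | 0.93 | 0.98 |
| post SD 0.8 × baseline | 0.59 | 0.65 | 0.66 | 0.63 |
| post SD 1.25 × baseline | 0.92 | 1.01 | 1.03 | 0.98 |

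Where the change score has 80% power (noncentrality 2.889, 32 df), ANCOVA on 31 df has 80.6 to 88.9%, 93.1 to 95.4% and 78.6 to 83.0% in the three rows. With equal SDs, ANCOVA has the smaller expected variance unless rho exceeds 2/(1 + 1/30) - 1 = 0.935.

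**3. The most it can cost.** Change variance minus residual variance is 1 + k² - 2·rho·k - k²(1 - rho²) = (1 - rho·k)², which is never negative. So the ratio cannot exceed 1 + 1/(N-4), whatever rho and k are. The bound does depend on the number analysed:

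| N analysed | 43 | 34 | 30 | 24 |
|---|---|---|---|---|
| largest expected variance loss | 1/39 = 2.6% | 1/30 = 3.3% | 1/26 = 3.8% | 1/20 = 5.0% |

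At 34, allowing also for the lost degree of freedom (squared critical value up by a factor of 1.0025), the interval is at most √(1.0333 × 1.0025) = 1.018 times as wide.

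**4. Chance imbalance at 17 per arm.** A baseline gap is non-significant on the t test up to 2.037 × √(2/17) = 0.70 SD. A gap of 0.5 SD gives p = 0.15, and a gap at least that large arises by chance in about 14% of trials. With equal SDs it shifts the change-score difference by (1 - rho) × 0.5 = 0.25, 0.15, 0.10 and 0.05 baseline SD.

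Simulated error with no true effect, 200,000 trials per correlation, equal SDs:

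| | rho 0.5 | 0.7 | 0.8 | 0.9 |
|---|---|---|---|---|
| change score, gap fixed at 0.5 SD | 7.6% | 6.8% | 6.1% | 5.6% |
| change score, gap fixed at 0 | 2.5% | 3.4% | 3.9% | 4.6% |
| ANCOVA, gap fixed at 0.5 SD | about 5% | about 5% | about 5% | about 5% |

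For the 0.5 SD gap, the change-score error is 8.6 to 9.1% with k = 0.8 and 5.0 to 6.3% with k = 1.25. Averaged over all gaps it is 5%.

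**5. The eta-squared label.** Within the repeated-measures ANOVA at N = 34, eta-squared 0.14 means F(1,32) = 0.14/0.86 × 32 = 5.21, p = 0.029. So a large label cannot sit beside a non-significant p if ANCOVA is a slip. That holds down to 28 analysed; at 27, F(1,25) = 4.07 and p = 0.054. If a real post-on-baseline ANCOVA was meant, the same mean difference would turn 0.06 into about 0.078 and 0.14 into about 0.178 at rho 0.5 with equal SDs.

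**The case against.** The strongest reply is that the planned test is legitimate. It already removes each woman's own baseline and holds its error rate over randomisation. The gain from ANCOVA rests wholly on correlations and SDs that the documents do not give, and in part of the grid there is no gain. All of that stands. A reader might infer that the plan's comparison is biased or invalid; the documents do not support that, since a gap of zero pulls the error below 5% as a large gap pushes it above.

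A reader might also infer that the SAP draws its p value and effect size from two genuinely different models. A post-on-baseline ANCOVA has no time x group term, so ANOVA is the natural reading and the correction is one word.

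Nor do the arm-specific Wilcoxon tests contradict the interaction test. A test run inside one arm can only be a pre-post comparison. What is missing is a statement to that effect and a between-arm rule.

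The SAP does not present the baseline t test as a safeguard, so the 0.70 SD figure shows only that the test cannot stand in for adjustment.

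Finally, switching models when results may already be known adds an analytic choice. That also stands, and it is met by labelling. None of this removes the core point: a baseline already in hand is left out of the model, and the most that using it can cost is small.

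**Conclusion.** The point holds as one of precision and of robustness to chance imbalance. With equal SDs and a correlation of 0.5 to 0.9, adjustment cuts the variance by about 2 to 22% at 34 analysed. Across the SD ratios tried, the range is 41% less to 3.3% more.

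The 3.3% ceiling holds over correlation and SD ratio but needs at least 34 analysed. The documents leave that number open, and the 43 against 17 + 17 should be reconciled.

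The conditional error figures assume intact randomised arms. The exclusion for adherence below 80% may break that, and ANCOVA does not repair it. The eta-squared attribution is a separate, minor wording defect. Overall this is a change that should be made; the plan is not unsound without it.

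**What to change.** - For each continuous outcome, make the between-arm test an ANCOVA of the post value on arm with the baseline value as covariate. Report the adjusted difference, 95% CI, p value and partial eta-squared for the arm term from that one fit.
- Keep the within-arm pre-post changes (the Sidak comparisons and the arm-specific Wilcoxon tests) as description only.
- Analyse any outcome that fails normality, such as Tg, by the same method in both arms, for example ANCOVA on the log scale.
- Leave the chi-square comparison of non-responders as a separate analysis.
- If the repeated-measures ANOVA is kept instead, take the eta-squared from it and replace ANCOVA with ANOVA.
- If the data are already analysed, as the past tense suggests, report the ANCOVA as post hoc beside the repeated-measures ANOVA.

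Cost: SAP wording, one refit per outcome on data already collected, one error degree of freedom, and a small added post hoc choice if results are known. In the worst expected case at 34 analysed, a comparison with 80% power would have 78.6%.
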